#### **6** STUDY INTERVENTION

#### 6.1 STUDY INTERVENTION(S) ADMINISTRATION

#### 6.1.1 STUDY INTERVENTION DESCRIPTION

Determination of metabolic rate by the metabolic cart (noninvasive connection of the device to the ventilator for 20 minutes). Initiate hypothermia (established Northwell hypothermia status post cardiac arrest protocol) using the Arctic Sun. Gel pads will be placed on subject body to cover at least 40% of body surface area. The inner layer of gel pad is made up of a heat conductive hydrogel that changes temperature and sticks to the skin. The middle layer of the pad has channels through which water is circulated and the outer layer is designed to insulate the circulating water, allowing it to maintain a temperature. Using sterile technique, a clinician will insert a temperature probe into subjects' bladder. The machine essentially is a cooling blanket. Many clinicians would use ice bags to cool patients, however using the machine allows for more accurate temperature monitoring and precision with the cooling process. The Arctic Sun 5000® is set to a temperature of 34.5 C to lower the body temperature.

Duration of hypothermia will be 48 hours after which the subject will be rewarmed. Metabolic rate, or indirect Calorimetry, will be assessed at baseline, day 1 of hypothermia, day 2 of hypothermia before rewarming, and after full rewarming. CBC, basic metabolic profile, magnesium, phosphorus, coagulation profile, ABG, inflammatory markers would be drawn every 12 hours during hypothermia until subject has achieved full rewarming and once after full rewarming.

The entire hypothermia procedure will last 48 hours. The length of time it takes to cool the patient is a maximum of 3 hours. Once the desired temperature is reached that temperature will be maintained as tolerated by subject. The new temperature of 36.5C will be manually entered into the machine initiating re-warming. Acceptable rewarming range is a temperature of 36.5C to 37.5C. The subject body temperature rewarming is typically set over 6-8 hours. Therefore, the final 6-8 hours of the 48 hour time period is set to rewarm the subject.

### 6.1.2 DOSING AND ADMINISTRATION

N/A

### 6.2 PREPARATION/HANDLING/STORAGE/ACCOUNTABILITY

### 6.2.1 ACQUISITION AND ACCOUNTABILITY

North Shore University hospital has six (6) Arctic Sun 5000® Machines. They will be obtained through materials management when a study patient is identified and consented. The machines are maintained on a regular basis as outlined in the Northwell Health System Medical Equipment Management Plan (MEMP) issued by the Biomedical/ Clinical Engineering Departments.

6.2.2 FORMULATION, APPEARANCE, PACKAGING, AND LABELING

Version <1.0.> <18 May 2020>

Application of mild hypothermia for COVID patients IRB# 20-0287

# 6.2.3 PRODUCT STORAGE AND STABILITY

The purpose of the Medical Equipment Management Plan (MEMP) is to assess and control the clinical and physical risks of fixed and portable equipment used for the diagnosis, treatment, measuring/monitoring, and the care of patients. The MEMP is designed to identify which items in the inventory of clinical equipment will be included in the management plan, and to establish minimum inspection standards for the identified equipment. The Director/Manager of Biomedical Engineering uses manufacturer recommendations, applicable codes and standards, accreditation requirements, and local or hospital experience to determine the appropriate maintenance strategy for assuring safety and maximizing equipment availability and service life. The strategies may include predictive maintenance, reliability-centered maintenance, interval-based inspections, corrective maintenance, or metered maintenance to ensure reliable performance.

### 6.2.4 PREPARATION

N/A

#### 6.3 MEASURES TO MINIMIZE BIAS: RANDOMIZATION AND BLINDING

N/A

#### 6.4 STUDY INTERVENTION COMPLIANCE

Application of mild hypothermia for COVID patients IRB# 20-0287

Hypothermia protocol will be initiated in the intensive care unit setting. A daily log will be kept documenting patient status throughout the course of cooling. In addition, an accurate account of time of hypothermia induction will be documented, vitals every 15 minutes during induction for the first hour and every hour thereafter. Subject's hemodynamic stability will be monitored regularly, at least hourly, including blood pressure and heart rate. The ventilator settings required will be documented as well. In addition, medications given to subject during the course of cooling will be documented.

# 6.5 CONCOMITANT THERAPY

N/A

# 6.5.1 RESCUE MEDICINE

Routine FDA approved medications for pain and sedation, such as Fentanyl, Dilaudid, Versed, Ketamine or Precedex may be administered to make the subject more comfortable during the course of cooling and to treat any shivering. These medications will be administered through an intravenous line. Expected body reactions to cooling include shivering and administration of such medications would not be considered treatment for an adverse event.

A paralytic infusion such as cisatracurium or rocuronium may rarely be necessary for shivering. A lot of patients, however, are already paralyzed due to their critical illness.

# 7 STUDY INTERVENTION DISCONTINUATION AND PARTICIPANT DISCONTINUATION/WITHDRAWAL

### 7.1 DISCONTINUATION OF STUDY INTERVENTION

Discontinuation from hypothermia protocol does not mean discontinuation from the study, and remaining study procedures should be completed as indicated by the study protocol. If a clinically significant finding is identified (including, but not limited to changes from baseline) after enrollment, the investigator or qualified designee will determine if any change in participant management is needed. Any new clinically relevant finding will be reported as an adverse event (AE).

The data to be collected at the time of study intervention discontinuation will include the following:

- Vitals including blood pressure, heart rate and temperature, indirect Calorimetry
- Labs as outlined in the SoA- CBC, magnesium, BMP, phosphorus, ABG, coagulation panel (coags) and inflammatory markers
- Ventilatory Settings- oxygen percentage, respiratory rate setting, tidal volume and positive end expiratory pressure (PEEP)

# 7.2 PARTICIPANT DISCONTINUATION/WITHDRAWAL FROM THE STUDY

Participants are free to withdraw from participation in the study at any time upon request. An investigator may discontinue or withdraw a participant from the study for the following reasons:

- If any clinical adverse event (AE), laboratory abnormality, or other medical condition or situation occurs such that continued participation in the study would not be in the best interest of the participant
- Disease progression which requires discontinuation of the study intervention
- If the participant meets an exclusion criterion (either newly developed or not previously recognized) that precludes further study participation
- Participant unable to receive hypothermia protocol for 48 hours

The reason for participant discontinuation or withdrawal from the study will be recorded on the Study Withdrawal Case Report Form (CRF).

The hypothermia protocol will be discontinued and full rewarming will be initiated prior to 48 hours if the following conditions occur: (1) hemodynamically unstable arrhythmia, (2) severe bradycardia (< 40bpm), (3) MAP less than 60mm Hg while on more than one vasopressor after resuscitation, (4) severe bleeding.

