# **3** OBJECTIVES AND ENDPOINTS

OBJECTIVES	ENDPOINTS	JUSTIFICATION FOR ENDPOINTS
Primary		
To determine if the application of mild hypothermia will decrease the patient's metabolic demand and improve carbon dioxide and oxygenation levels	
 
(1) Changes in resting metabolic rate during and after hypothermia
 
(2) Changes in arterial pO2 during and after hypothermia
 
(3) Changes in arterial pCO2 levels during and after hypothermia
 
	Resting metabolic rate is considered the gold standard way to measure metabolic demand. Arterial pO2 and pCO2 are the accepted measurements for oxygen and carbon dioxide levels.
Secondary		
To determine if the application of mild hypothermia reduces the pro- inflammatory response to COVID- 19	Changes in CRP, ESR, D-Dimer, Ferritin, during and after hypothermia.	CRP, ESR, D-Dimer, and Ferritin are inflammatory markers that are have been demonstrated to be elevated in patients with COVID-19 and have been correlated to severity of disease

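### Section 7.1 keeps early stoppers in the study while 7.2 allows the investigator to withdraw them, so the after-rewarming comparison with baseline may omit patients who tolerated cooling poorly

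*Combined protocol and SAP*

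**What the plan says.** Section 7.1 sets the default: "Discontinuation from hypothermia protocol does not mean discontinuation from the study, and remaining study procedures should be completed". It also requires an assessment at the moment of stopping ("The data to be collected at the time of study intervention discontinuation will include the following"), covering vitals, indirect calorimetry, laboratory tests including ABG and inflammatory markers, and ventilator settings.

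Section 7.2 opens its list with "An investigator may discontinue or withdraw a participant from the study for the following reasons". Two of the listed reasons are "Participant unable to receive hypothermia protocol for 48 hours" and "Disease progression which requires discontinuation of the study intervention". The reason is recorded on a study withdrawal form. The same section lists four conditions that end cooling before 48 hours, and 10.1.6 lists safety events that also lead to rewarming.

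The first primary endpoint in section 3 is "Changes in resting metabolic rate during and after hypothermia", and the pO2 and pCO2 endpoints cover the same window. Section 6.1.1 schedules calorimetry at baseline, on day 1, on day 2 before rewarming, and after full rewarming. Section 9.2 fixes 20 attempts without replacement, 9.3 puts every enrolled patient in every analysis, and 9.4.2 compares each later time point with baseline by a Wilcoxon rank sum test.

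**The concern.** One event, cooling stopped before its planned end, triggers two rules with different consequences for data collection. Under 7.1 the patient goes on to the after-rewarming assessment. Under 7.2 the investigator may end participation, and that assessment is not made. The choice is left to case-by-case judgement, in patients selected because they did not tolerate cooling or were getting worse.

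With 20 patients, no control arm and no replacement, the after-rewarming comparison would then describe mainly those who tolerated the intervention. Sections 9.3 and 9.4 do not say how a missing later value is handled or how the 7.1 stopping assessment enters the analysis. Values never collected cannot be recovered afterwards, so this has to be settled in advance.

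**Working it through.** The plan has no figure to reproduce: 20 is a chosen number, with no alpha, power, SD or dropout rate. The check is mainly a comparison of text.

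**Step 1: do the two rules meet in the same patients?** Section 6.1.1 uses 48 hours in two ways: "Duration of hypothermia will be 48 hours after which the subject will be rewarmed", and "the final 6-8 hours of the 48 hour time period is set to rewarm the subject". On the second reading, rewarming starts at about hour 40 to 42 (48 − 8 to 48 − 6). A stop before scheduled rewarming falls short on either reading. Every early safety stop in 7.2 and 10.1.6 therefore meets the 48-hour ground and also falls under 7.1.

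**Step 2: does anything rank the rules?** No. Reading the 7.2 list as concerning treatment only does not work, because its opening sentence refers to the study and a study withdrawal form is used.

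**Step 3: what does the 7.2 discretion itself remove?**
- After-full-rewarming value: removed. Calorimetry is the clearest loss. For pO2 and pCO2 it depends: 10.1.3 and 10.1.9.1 say laboratory values are collected routinely and held in the medical record, but not whether they may be used after withdrawal.
- Day 2 before-rewarming value: not removed by 7.2. A patient already rewarmed cannot supply it even if retained. The 7.1 stopping assessment partly stands in, at an earlier time.

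**Step 4: illustration of size.** All inputs except n = 20 and the three primary endpoints are assumptions. Let k be the number withdrawn, treating every early stopper as withdrawn and no value as recoverable.
- Upper count of missing after-rewarming primary values = 3k of 3 × 20 = 60.
- Outer limit on the gap in mean paired change between those kept and all 20, in sample SDs of change = √(k/(20 − k)) × √(19/20). It is reached only if all lost patients share one value and all kept patients another.
- Expected shift = r × m. Here r is an assumed correlation between tolerance and favourable change (−0.3 to 0.7), and m is the mean of the normal order statistics kept after dropping the k lowest of 20 (0.182, 0.333, 0.476).

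| k | kept | missing, at most | outer limit (SD) | expected shift (SD), r = −0.3 to 0.7 |
|---|---|---|---|---|
| 2 | 18 | 6 of 60 | 0.32 | −0.05 to +0.13 |
| 4 | 16 | 12 of 60 | 0.49 | −0.10 to +0.23 |
| 6 | 14 | 18 of 60 | 0.64 | −0.14 to +0.33 |

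At r = 0 the expected shift is zero. Section 9.1 gives a 10% figure for metabolic rate, read here as a 10% decrease. With k = 6 and an assumed SD of percent change of 5 points, the shift is −0.7 to +1.7 points. At an SD of 15 points it is −2.1 to +5.0 points.

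These figures describe mean paired change. The planned rank sum test is unpaired and could keep withdrawn patients' baselines, so they do not describe that test. No error rates are claimed, since the plan states no alpha.

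**Step 5: is an early stop likely at all?** If each patient independently had an assumed 10% chance of stopping early, the chance of at least one among 20 is 1 − 0.9^20 = 0.878. That is the chance of an early stop, not of a withdrawal.

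**The case against.** The best defence is that a default and a discretion can coexist. Section 7.2 is permissive, and its paragraph on safety stops speaks of discontinuing the hypothermia protocol, which is the situation 7.1 addresses. Section 4.4 defines completion by the last scheduled test, and 9.2 and 9.3 point to retention. This stands in part: it makes withdrawal less likely and lowers the severity. It does not settle which rule applies, and 9.3 cannot supply values that were not collected.

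It is also fair to say that some values would be missing under any wording, through death or through the conditions in 5.2 item 5 that preclude calorimetry (renal replacement therapy, ECMO, chest tube). The counts above do not separate these, so they overstate what a rewording can recover. The lack of a missing-value rule in 9.3 and 9.4 is likewise a gap of its own, whatever 7.2 says.

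Four stronger readings are tempting, and the documents do not support them:
- A reader might infer that early stoppers must be withdrawn. Section 7.2 only permits it.
- A reader might infer that the omission favours hypothermia. That needs stoppers to do worse on these endpoints, and nothing in the documents links tolerance to change in metabolic rate, pO2 or pCO2.
- A reader might blame 7.2 for the lost day 2 value. Stopping cooling removes it.
- A reader might infer that early stops would be hidden. The withdrawal form, the adverse event records (8.3.4) and the individual listings (9.4.8) keep them visible.

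**Conclusion.** The concern holds in a limited form. Sections 7.1 and 7.2 give different consequences for the same event and are not ranked. If the 7.2 discretion is used, the after-rewarming comparison with baseline may leave out patients who tolerated cooling poorly, contrary to 9.3. The effect is confined to efficacy comparisons after rewarming.

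Its direction and size are unknown. The SD and percentage-point figures rest wholly on assumed withdrawals, correlation and SD, and the ranges include zero. The missing-value counts are upper limits. For an uncontrolled pilot with individual listings this is minor to moderate, but worth correcting because it is cheap and must be done beforehand.

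**What to change.** Reconcile 7.1 and 7.2 so that neither receiving less than 48 hours of hypothermia nor disease progression that stops the intervention is by itself a ground for ending data collection. Remaining scheduled measurements, the after-rewarming assessment in particular, continue unless consent is withdrawn, the existing best-interest ground in 7.2 applies, or a measurement is not feasible (for example, calorimetry under a condition in 5.2 item 5). The change concerns data collection only: no rule on when cooling is stopped is added or altered.

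In 9.3 and 9.4, report the number contributing at each time point. Identify early stoppers' values, and the 7.1 stopping assessment, separately from values taken during hypothermia, so that short and full exposure are not mixed unmarked. State whether routine record values may be used after an investigator withdrawal.

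The cost is a few sentences, minor reporting work, and for each early stopper at most three further 20-minute calorimetry sessions (days 2, 3 and 4) with bloods, all already in the Schedule of Activities.

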# 7.3 LOST TO FOLLOW-UP

N/A

# 8 STUDY ASSESSMENTS AND PROCEDURES

### 8.1 EFFICACY ASSESSMENTS

Patients admitted to the critical care unit who remain on ventilator support will be screened by the research team for eligibility. Qualifying patients' will be considered and their LAR contacted by an IRB approved investigator authorized to obtain informed consent. Once informed consent obtained as outlined, study data will be collected as documented in Section 1.3 Schedule of Activities (SoA). Data for research protocol will be collected as outlined below by a study member who is authorized by IRB and trained to the protocol.

- **Demographics:** At screening/baseline demographic data collected will include name, MRN, age and sex
- Medical History: documentation of prior medical history
- **Physical examination:** daily targeted exam highlighting the location and placement of pads
- Indirect Calorimetry- gas exchange information collected from the mechanical ventilator to calculate the metabolic rate
- Hypothermia Protocol- subject is connected to the Arctic Sun 5000®, an FDA approved temperature management system. Gel pads will be placed on subjects' body to cover at least 40% of the body surface. The gel pads are soft, pliable and stick to the skin; the inner layer is made up of a heat conductive hydrogel that changes temperature and sticks to the skin. The middle layer of the pad has channels through which water is circulated and the outer layer is designed to insulate the circulating water, allowing it to maintain a temperature. Using sterile technique, a licensed and trained clinician will insert a temperature probe into subjects' bladder. The Arctic Sun 5000® is set to lower the body temperature to 34.5C. The machine will be set to reduce the body temperature by 0.5 degrees C per hour to complete the cooling period within a 3 hour time period. Vitals will be monitored continuously and charted every 15 minutes for the

first hour then every hour thereafter. Once the desired temperature is reached that temperature will be maintained as tolerated by subject. Once the cooling period is completed, the new temperature of 36.5C will be manually entered into the machine initiating re-warming. Acceptable rewarming range is a temperature of 36.5C to 37.5C. The subject body temperature rewarming is typically set over 6-8 hours. The body will be rewarmed at a rate of 0.25 degrees C an hour. Therefore, the final 6-8 hours of the 48 hour time period is set to rewarm the subject. The subject will be connected to the machine by a certified and trained clinician (nurses trained to use the Arctic Sun 5000® which is essentially a cooling blanket).

- Medications: routine FDA medications for pain and sedation, such as fentanyl, dilaudid, versed, ketamine and/or precedex may be administered as needed to make the subject comfortable during the cooling and to treat any shivering. Routine medications are administered via an IV line by trained and licensed medical practitioners who are trained to assess medical events. Potential medications to be administered for symptoms related to hypothermia include paralytic infusions such as cisatracurium or rocuronium. These drugs are FDA approved medications; side effects of rocuronium include rash, nausea, vomiting and changes in blood pressure both high and low. Side effects of cisatracurium include slow heart rate, dizziness and redness or flushing of the skin. Patients remain on continuous monitoring when these infusions are used; also, all patients in the critical care unit and those included in this study are monitored continuously.
- Laboratory Assessments: blood work will be collected at screening and baseline and every 12 hours while hypothermia protocol in course including complete blood count (CBC), basic metabolic panel (BMP), coagulation panel (coags), arterial blood gases (ABGs), inflammatory markers including D-dimer, ferritin, c reactive protein (CRP) and erythrocyte sedimentation rate (ESR). These blood specimens are collected as part of the analysis to evaluate the oxygenation and carbon dioxide production while on the hypothermia cooling protocol and during rewarming. Additionally, blood will be tested for levels of inflammatory marker assessment, white blood cell count and electrolytes assessment. Blood samples will be collected from the central lines already inserted in the critically ill patient and there will be no requirement for additional sticks for blood draws required for research analysis.
- Ventilator Settings:- ventilator modes and settings to be documented including percent oxygen delivered, set respiratory rate, tidal volume set (if on volume control ventilation) and tidal volume delivered by patient, set pressure support (if on pressure support ventilation), the set positive end expiratory pressure (PEEP), plateau pressures. The hypothesis is that hypothermic protocol may offer overall improvement in oxygenation and ventilation status and perhaps clinicians will be able to decrease the amount of ventilator support.
- **Primary Endpoint-** lab specific to primary endpoint includes serial ABGS as outlined in SoA; ABG will be collected every 12 hours. Arterial Blood Gas (ABG) will document the oxygenation and the amount of carbon dioxide in patient serum. Indirect calorimeter measurements will also be compared.
- Secondary Endpoint- laboratory assessments specific to secondary endpoint include the collection of inflammatory markers as outline above (ESR, Ferritin, D-Dimer and ESR) every 12 hours.

# 8.2 SAFETY AND OTHER ASSESSMENTS

Patients enrolled in the protocol are monitored continuously while on the hypothermic protocol to verify and assure that the patient is tolerating the protocol. The patients are managed in critical care

units by a critical care team and the investigators on this study will evaluate the patient daily for AEs and SAEs as well as any unanticipated problems (UPs).

- **Physical examination** daily assessments are captured per standard of care. Any other changes in physical exam related to cooling protocol will be documented including symptoms of shivering.
- **Vital signs** temperature will be documented continuously during the initial stages of cooling, every 15 minutes for the first hour and then hourly thereafter. Other vitals to assure hemodynamic stability include heart rate and blood pressure.
- Electrocardiograms (EKGs): will be collected only in the event of an AE or SAE; specifically if it is noted that the patient has any bradycardia or any other type of new onset arrhythmia, then the clinician will obtain a 12 lead EKG
- Assessment of adverse events. The patients enrolled in this study are cared for in critical care units and therefore have continuous nursing monitoring per routine care. The investigator who is IRB approved will round regularly while patients' are on this cooling protocol. AE and SAEs will be documented accordingly and subject treated per standard of care based on the adverse event.

